CGI-S	Clinical Global Impression-Improvement
CHI-I	Clinical Global Impression-Severity
CYBOCS-PPD	Children’s Yale-Brown Obsessive Compulsive Scale-Pervasive Developmental Disorders
KADI	Krug Asperger’s Disorder Index
Leiter-R Brief IQ	Leiter International Performance Scale-Revised Brief Intelligence Quotient Screener
M50	The ~50ms component of the auditory

	evoked neuromagnetic field
M100	The ~100ms component of the auditory evoked neuromagnetic field
MEG	Magnetoencephalography
MMF	Mismatch field
MRI	Magnetic Resonance Imaging
MRS	Magnetic Resonance Spectroscopy
ODT	Optimal Dose Tolerability
PK	Pharmacokinetics
Placebo	Placebo Condition
PPVT-IV	Peabody Picture Vocabulary Test-Fourth Edition
RBANS	Repeatable Battery for the Assessment of Neuropsychological Status
RBS	Repetitive Behavior Scale
RT	Reaction time
RTP	Rapid Temporal Processing
SB5	Stanford-Binet Intelligence Scale–5th Edition
SCQ	Social Communication Questionnaire-Current and Lifetime versions) [parent completed measure]
SMURF	The Safety Monitoring Uniform Report Form
SRS-II	Social Responsive Scale, 2nd edition) [parent completed measure]
TID	Three times a day
VABS-II	Vineland Adaptive Behavior Scales [parent/caregiver rating form]
VAS-Target Behavior	Parent Defined Target Symptoms Scale-Visual Analog Scale
WASI-II	Wechsler Abbreviated Scale of Intelligence – 2nd Edition

ABSTRACT

Context: (Background)

Magnetoencephalographic (MEG) studies in autism spectrum disorders (ASD) have pointed to neural oscillation abnormalities.

Objectives: (primary and important secondary objectives)

A candidate therapeutic for ASD has been developed – STX209, a GABA-B agonist. STX209 targets synaptic activity that has clear electrophysiological correlates. This proposal assesses the responsiveness of neural oscillatory measures to acute administration of STX209.

Primary Objectives:

1. Determine whether STX209 produces a dose-dependent significant change in MEG target parameters compared to baseline as well as compared to placebo treatment.
2. Determine whether STX209 leads to a dose-dependent significant change in magnetic resonance spectroscopy (MRS)-obtained auditory cortex GABA levels compared with placebo treatment.

Study Design:

A ‘randomized’ acute dose-response design

Setting/Participants:

All imaging is performed at the Children’s Hospital of Philadelphia. Participants will be forty male adolescent individuals (14- to 17.75-years-old) with an ASD diagnosis.

Study Interventions and Measures:

Each participant will receive (in increasing order) doses of 15mg and 30mg of STX209, with a single placebo treatment randomly administered (i.e., placebo exam could be first, second, or third exam). For the MEG primary target parameters are bilateral auditory cortex resting state gamma power and auditory evoked gamma power and synchrony as well as auditory evoked 100ms “M100” response latency. For MRS target parameters are bilateral auditory cortex GABA.

PROTOCOL SYNOPSIS

Study Title	MEG/MRS Dose Response Study of STX209 in ASD
Funder	Simons Foundation
Clinical Phase	Exploratory study for MEG
Study Rationale	
Recent evidence from magnetoencephalographic (MEG) studies in ASD have pointed to abnormalities (specifically, delays) in auditory evoked neuromagnetic responses (e.g. M100 – see Roberts et al., 2010, and mismatch field, MMF – see Roberts et al., 2011) as well as abnormalities in the oscillatory behavior of auditory cortex, especially in the gamma band (30-50Hz), at rest and in response to simple auditory stimuli (see Gandal et al., 2010 and Cornew et al., 2012; Edgar et al., 2013). The local circuitry underlying such evoked activity and oscillations, and synaptic transmission, in general, requires an appropriate balance of excitation and inhibition, mediated by glutamate and GABA, respectively. One model of the neural oscillatory deficits in ASD suggests that impaired regulatory control by inhibitory interneurons onto pyramidal cells underlies abnormal auditory latency and oscillatory electrophysiological measures. As such, electrophysiological deficits are interpreted in terms of local circuitry abnormalities, with inferences at the molecular level of imbalances in the activity of glutamate and GABA.
 
A candidate therapeutic for ASD has been developed – STX209, a GABA-B agonist. Since this pharmaceutical targets synaptic activity that has clear electrophysiological correlates, one goal of this proposal is to assess the responsiveness (sensitivity to change) of MEG measures to acute administration of STX209 at various doses in adolescents on the autism spectrum. The study also aims to establish the nature of the putative relationship between such electrophysiologic markers and GABA and glutamate levels using MEGAPRESS spectrally-edited magnetic resonance spectroscopy (MRS).

Study Objective(s)	
 1. To determine whether STX209 produces a significant change in MEG target parameters compared to baseline as well as compared to placebo treatment. Secondly, to determine if the magnitude of such change is influenced by STX209 dose: 0 mg (placebo) versus 15mg versus 30 mg. 2. To determine whether STX209 leads to a significant change in MRS-obtained auditory cortex GABA levels compared with placebo treatment. Secondly, to determine whether the magnitude of the GABA change is influenced by STX209 dose level. 3. To determine if dose-dependent changes in MEG target parameters are correlated to dose-dependent changes in MRS target parameters in auditory cortex.
Test Article(s) (If Applicable)	STX209 (Arbaclofen), a GABA-B agonist and a matching placebo. The active compound is made available to this project by the Clinical Research Associates, LLC (CRA).

Study Design	A randomized acute dose-response design will be employed with a total study duration of 3 weeks. At each visit, baseline MEG will be obtained followed by acute single-dose drug/placebo administration, followed 60 minutes later by repeat MEG. Each participant will receive a single dose of placebo in random order and a single dose of STX209 from smallest to largest (15mg and 30mg). MRI and MRS will be performed immediately following MEG to provide an anatomic basis for source localization as well as to assess acute effects of STX209 administration on MRS estimates of GABA and glutamate.
Number Of Subjects	This is a single site study. 40 male subjects with ASD will be recruited in order to get 38 evaluable subjects.
Study Duration	Subjects will be examined at three separate sessions, at each session receiving in random order a single-dose of placebo, and from smallest to largest a single-dose of STX209 (15mg and 30mg). Each subject's participation will last approximately 4 weeks although participation could be extended up to six or eight weeks if subjects are unable to come four consecutive weeks in a row. The entire study is expected to last one year.
Study Phases	
Screening	Screening for eligibility, obtaining consent, and cognitive and clinical symptom assessments
MEG Assessments	Over a period of 3 visits (at least 1 week apart), baseline MEG exam and then MEG/MRS assessment of STX209 at 15mg and 30mg doses or a single placebo.
Efficacy Evaluations	The measures used to assess efficacy of STX209 will be as follows: 
 1. Change from baseline to STX209 administration in left and right superior temporal gyrus auditory M50, M100 and MMF latencies. 2. Change from baseline to STX209 administration in left and right superior temporal gyrus auditory gamma total power and phase-locking measures (examined pre- and post-stimulus).
Safety Evaluations	All safety evaluations will be done by the study physician [name], a Developmental-Behavioral Pediatrician at the Children's Hospital of Philadelphia. The Safety Monitoring Uniform Report Form (SMURF) will be used to assess STX209 specific side effects. In addition, safety and tolerability of STX209 will be determined by Adverse Events (AE), Vital Signs (heart rate and blood pressure), and a blood draw for BUN and creatinine labs. [name] or one of her attendings will be on call for any problems that might arise in between study visits. Families will be advised to call 911 in case of an emergency when they are not at our Center.
Statistical And Analytic Plan	Primary statistical analyses assess baseline versus post acute-dose (placebo, STX209 15 and 30 mg) changes for (1) M100 auditory latency, and (2) post-stimulus auditory gamma-band activity. For each dependent measure, ANOVAs with dose as a repeated measure will examine baseline versus post acute-dose changes (analyses showing no significant differences across time in baseline M100 and gamma measures will allow

	
use of a single averaged baseline measure). Contrasts of a priori interest assess (1) a baseline versus post-acute dose change in the dependent measures averaging across STX209 15 and 30 mg, as well as (2) a change in dependent measures from baseline versus STX209 15 mg versus STX209 30 mg, with this test demonstrating an effect of dose. Given the possibility of between-subject variability in the degree of baseline auditory neural pathology, analyses will also examine response to treatment in those participants showing the greatest baseline auditory neural circuit abnormality (median split on M100 latency or gamma power), with a larger effect of treatment expected in those participants showing greater baseline auditory neural impairment. Secondary and exploratory analyses examine baseline to post acute-dose response changes in MRS auditory GABA concentration as well as associations between MEG functional measures and MRS GABA concentration.

DATA AND SAFETY MONITORING PLAN	
The investigators will perform the study in accordance with this protocol, will obtain consent and assent (unless a waiver is granted), and will report unexpected problems in accordance with CHOP and federal requirements. Collection, recording, and reporting of data will be conducted to ensure the privacy, health, and welfare of research subjects during and after the study. Any episode of noncompliance will be documented in the CRF.
 
Upon entry to the study, all subjects will be given a study identifier code. This code will be used in all data acquisition (MEG and MRS). During the study, the association between subject name and identifier will be kept in a electronic database with restricted encrypted access only (i.e., CHOP SAN drive). MEG and MRS data will be archived to permanent storage on the secure CHOP SAN drive. Hardcopy consent forms will be stored in a locked file cabinet located in [name] office.
 
The Office of Research Compliance and Regulatory Affairs (ORCRA) at CHOP will conduct routine data safety monitoring of this sponsor-investigator trial. A data safety monitoring plan will be developed before the first subject is enrolled and will be maintained in the regulatory file for the study. Data monitoring will include informed consent form review, regulatory documentation review, source data verification and case report form data validation, sponsor documentation review and drug accountability. The frequency of monitoring may be modified as needed based on previous monitoring outcomes and/or rate of enrollment.

TABLE 1: SCHEDULE OF STUDY PROCEDURES

[figure not shown]
Study Phase	Phone-Screen	Screening Visit	MEG Assessment		
Visit Number			Visit 1*	Visit 2*	Visit 3*
Study Days	pre	0	7	14	21
Phone screen / Eligibility / Verbal Informed Consent	X				
Pre-visit Intake Questionnaire	X				
Written Informed Consent/Assent		X			
Phone Parent Informed Consent	X				
Review Inclusion/Exclusion Criteria		X			
Demographics/Medical History		X			
Intervention History Form					
Prior/Concomitant Medications		X			
The Safety Monitoring Uniform Report Form (SMURF)		X	X	X	X
Vital Signs		X	X	X	X
Physical Examination		X			X
Blood Draw**		X			
Autism Diagnostic Observation Schedule (ADOS-II)		X			
Autism Diagnostic Interview-Revised (ADI-R)		X			
Child Behavior Checklist (CBCL)		X			
Clinical Evaluation of Language Fundamentals (CELF –IV)		X			
DSM-IV Checklist of Autism Symptoms		X			
Repetitive Behaviour Scale (RBS)		X			

Social Communication Questionnaire (SCQ)		X			
Social Responsive Scale (SRS-II)		X			
Vineland Adaptive Behaviour Scales (2 nd edition)		X			
Wechsler Abbreviated Scale of Intelligence (WASI-II)		X			
Randomization		X			
MEG Scan (pre/post drug administration)			X	X	X
MRI Scan			X	X	X
Dispense Study Drug			X	X	X
Adverse Event/Serious Adverse Event Assessment			X	X	X

NOTE: At each of the three visits, subjects will receive (in increasing order) doses of 15mg and 30mg of STX209 and a randomly administered single placebo exam. Each subject's participation will last approximately 3-4 weeks, although participation could be extended up to six or eight weeks if subjects are unable to come four consecutive weeks in a row. At each visit, baseline MEG will be obtained followed by acute single-dose drug/placebo administration, followed 60 minutes later by repeat MEG

*MEG Assessment visits will be scheduled no less than four days or more than 14 days apart.

** In cases where subject is unable to do a blood draw on the day of the screening visit due to anxiety/fear/discomfort if no medical risk factors are identified during medical history review, we will either accept BUN and Creatinine results from an outside source within 3 months of first imaging visit or attempt to do the blood draw on the day of the imaging visit

FIGURE 1: STUDY DIAGRAM

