5.6 Statistical Methods

Primary statistical analyses assess baseline versus post acute-dose (placebo, STX209 15 and 30 mg) changes for (1) M100 auditory latency, and (2) post-stimulus auditory gamma-band activity. For each dependent measure, ANOVAs with dose as a repeated measure will examine baseline versus post acute-dose changes (analyses showing no significant differences across time in baseline M100 and gamma measures will allow use of a single averaged baseline measure). Contrasts of *a priori* interest assess (1) a baseline versus post-acute dose change in the dependent measures averaging across STX209 15 and 30 mg, as well as (2) a change in dependent measures from baseline versus STX209 15 mg versus STX209 30 mg, with this test demonstrating an effect of dose. Secondary and exploratory analyses examine baseline to post acute-dose response changes in MRS auditory GABA concentration as well as associations between MEG functional measures and MRS GABA concentration.

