5.7 Sample Size and Power

Forty individuals with ASD (aged 14 to 18 years) will be recruited. In each individual, baseline and post acute-dose imaging data will be obtained at three doses: (1) placebo, (2) STX209 15 mg, or (3) STX209 30 mg. Imaging measures at these three doses will be obtained at least 1 week apart, with the order of placebo and STX209 pseudo-randomized with the constraint that the STX209 15mg dose will be administered before the STX209 30 mg dose (FDA requirement). Assuming lost data or incomplete data sets from 4 individuals, the following power calculations were performed assuming a final sample of 36. As detailed in Section 1.3, given significant between subject variability in auditory cortex neural circuit pathology and thus potential between subject differences with regard to normalization of brain activity in response to STX209, the below statistical analyses conservatively assume a response to STX209 from approximately 50% of the participants. As detailed below, although the study is sufficiently powered to assess a baseline versus a 'general' post acute-dose change (i.e., averaging 15mg and 30mg), there is insufficient data to determine if the study is powered to observe a difference between STX209 15mg and STX209 30mg acute dose brain responses. As such, present data will provide preliminary data to guide future studies investigating STX209 dose differences.

Regarding the primary aims, assuming baseline to post acute-dose changes in M100 latency of approximately 2.5 ms (5 ms = one-half the ASD and control group differences reported in Roberts et al. (2010) and in the range observed in the single Arbaclofen study patient (2-8ms), but half of 5 ms given acute responses in only 50% of the participants), and assuming a standard deviation of similar size (which may be conservative given initial cross-dose averaging), and assuming a response in only 50% of the population, given a sample of 36 and $p = 0.05$, the power to detect a main effect on M100 latency is equal to 0.80. Assuming baseline to post acute-dose changes in post-stimulus gamma-band activity approximately half that reported in Edgar et al. (2015), the power to detect a main effect on gamma activity is approximately 0.70.

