Given between subject variability in baseline auditory latency and gamma measures, and given a hypothesis that those participants showing the most pronounced M100 and gamma neural circuit pathology will show the largest response to STX209, the above analyses will be repeated with Group as a factor, with grouping obtained via a median split of M100 latency or gamma activity to identify those participants with more versus less auditory cortex neural circuit pathology. A Group X baseline to post acute dose interaction is expected, with significantly greater change observed in the more impaired ($N = \sim 18$) versus less impaired group ($N = \sim 18$). Given an expected greater effect in the participants showing greater impairment at baseline (e.g., a 5+ ms delay in the group showing greater auditory neural abnormalities), the study is powered at approximately 0.80 to observe an effect of this size.

Thus, the present study is sufficiently powered to assess the primary study aims.

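### The median-split subgroup analysis carries a power claim but has no stated status, no fixed split or test, and no error control

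*Combined protocol and SAP*

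**What the plan says.** **Synopsis, Statistical And Analytic Plan.** The row opens with the primary analyses and gives two a priori contrasts. It then announces a further step, to "also examine response to treatment in those participants showing the greatest baseline auditory neural circuit abnormality (median split on M100 latency or gamma power", and adds that a larger effect is expected where baseline impairment is greater. Only after that does it turn to secondary and exploratory work.

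**Section 5.7.** The main analyses are to be repeated with Group as a factor, splitting on M100 latency or gamma activity. "A Group X baseline to post acute dose interaction is expected, with significantly greater change observed in the more impaired" half, with about 18 participants in each. Power is put at about 0.80 for an effect of 5 ms or more. The next sentence reads "Thus, the present study is sufficiently powered to assess the primary study aims".

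**Sections 5.4, 5.6 and 5.6.2.** None mentions the split. Section 5.6 otherwise repeats the synopsis text, but goes straight from the contrasts to "Secondary and exploratory analyses examine baseline to post acute-dose response changes in MRS auditory GABA concentration".

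**Error rate.** The only significance level is in the whole-group power statement: "given a sample of 36 and $p = 0.05$, the power to detect a main effect on M100 latency is equal to 0.80". No multiplicity adjustment is described anywhere, and no level is given for the subgroup tests.

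**The concern.** Four things are left open.

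- **Status.** A statistician working from 5.6 would not run this analysis. One working from the synopsis or 5.7 could report it as a powered analysis belonging with the primary ones.
- **Split.** M100 and gamma are joined by *or*, and neither is tied to an outcome.
- **Test.** The synopsis describes response in the more abnormal half, while 5.7 describes an interaction. These can disagree.
- **Baseline.** The split variable is the same measurement from which change is calculated.

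The trial is built around uneven response: 5.7 assumes that about half the participants respond. If the whole-group tests are null, a responder subgroup is the natural next claim. The plan leaves several routes to it, and would allow a conclusion that STX209 normalises auditory responses in impaired participants when it does not.

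**Working it through.** **1. The plan's own 0.80.** Inputs from 5.7: the calculations were "performed assuming a final sample of 36"; 18 per half; 5 ms in the more impaired half; a whole-group change of 2.5 ms; an SD described only as of similar size. I assume no change in the less impaired half and a two-sided 0.05 test; 5.7 states neither.

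- Interaction noncentrality: 5 / (SD × √(2/18)) = 15/SD.
- Whole-group noncentrality: 2.5 × √36 / SD = 15/SD, the same.
- t-test power for the interaction: 1.00 at SD 2.5, 0.83 at SD 5, 0.80 at SD 5.2.

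The 0.80 is therefore close to what an SD of 5 ms gives and exact at 5.2 ms, but the SD used is not stated. Power is not the fault here.

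**2. The places side by side.**

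| Place | Split analysis present? | Test described | Status given |
|---|---|---|---|
| Synopsis | Yes, before the secondary analyses | Response in the more abnormal half; larger effect expected there | By position only |
| 5.4 | No | – | – |
| 5.6, 5.6.2 | No | – | – |
| 5.7 | Yes, with power | Group-by-change interaction | None; followed by the sentence on primary aims |

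**3. Size of the family.** For k independent tests at 0.05 the chance of at least one false positive is 1 − 0.95^k: 0.0975 for k = 2, 0.1855 for k = 4, 0.3366 for k = 8. These tests are dependent, so I simulated the null: 36 subjects, 18/18 splits, one M100 and one gamma change score, splits unrelated to change, 20,000 replicates. The correlation between the two split variables and that between the two outcomes were each set to 0, 0.5 and 0.8. These are assumptions.

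| Tests counted | Both correlations 0.5 | Range over nine settings |
|---|---|---|
| 2 interactions, split matched to outcome | 0.096 | 0.09 to 0.10 |
| 4 interactions, 2 splits × 2 outcomes | 0.168 | 0.14 to 0.19 |
| 8: those four plus four tests in the impaired half | 0.255 | 0.21 to 0.29 |

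For eight tests, six of the nine settings lie between 0.22 and 0.27. Testing the hemispheres separately would add tests.

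**4. Do the two tests agree?** With an identical effect of 0.5 SD (assumed) in both halves, 18 per half, the within-half test is significant in 52% of simulations and the interaction in 5%. A uniform effect could therefore be presented as subgroup-specific.

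**5. Regression to the mean.** Assume no drug effect, reliability r for one measurement (not given in the documents), total variance 1, change taken as the mean of the two post-STX209 values minus the mean of three baselines, and the split made on that same mean.

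- Covariance of change with the split variable: −(1 − r)/3.
- Slope: −[(1 − r)/3] / [r + (1 − r)/3]. At r = 0.8 this is −0.0667/0.8667 = −0.077; at r = 0.5, −0.1667/0.6667 = −0.25.
- The extreme half moves back towards the middle, which is the direction the plan predicts for treatment.
- Simulated rejection rate of one nominal 0.05 interaction: 0.07, 0.08, 0.13, 0.18 and 0.32 for r = 0.95, 0.9, 0.8, 0.7 and 0.5.

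**6. With placebo subtracted.** If the averaged baseline is used it cancels, leaving post-STX209 minus post-placebo. If each visit keeps its own baseline, the baseline errors enter the contrast with weights −1/2, −1/2 and +1, and the split with 1/3 each. The covariance is proportional to (−1/2 − 1/2 + 1)/3 = 0, given equal error variance across visits. Simulated rejection is about 0.05 at every r, either way.

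**7. Price in precision.** With independent errors only, and the error variance of one measurement as the unit:

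- Averaged baseline: from 1/2 + 1/3 = 5/6 to 1/2 + 1 = 3/2, so the standard error grows by √1.8 = 1.34.
- Visit-specific baselines: from 1 to 3, a factor of √3 = 1.73.

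**The case against.** Neither the synopsis nor 5.7 calls the split primary or confirmatory. The objectives in 2.1 and the endpoints in 5.4 contain no subgroup. Section 5.7 gives power for the primary aims as whole-group main effects, so its closing sentence need not cover the split. The synopsis also describes the study's phase as exploratory for MEG. A reader might infer that the plan makes the subgroup a confirmatory claim; the documents do not go that far. What stands is that its position invites that reading and nothing rules it out. The study-wide label does not rank this analysis.

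The split wording can be read respectively, M100 for M100 and gamma for gamma. The synopsis sentence goes on to a comparison that 5.7 makes specific as an interaction, and it specifies no separate significance test in the impaired half. On that reading there are two tests and a rate of about 0.10, the ordinary cost of two outcomes. This is fair. A reader might also take a figure near 0.26 as the plan's false-positive rate. That needs all eight combinations, which no section lists. Nor do the documents say that each subgroup test is run at 0.05; this is inferred from the one level given and the absence of any adjustment.

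Section 5.7 does state the interaction and its direction in advance, which limits freedom of choice. It does not limit regression to the mean, which acts in that same direction.

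**Conclusion.** The point holds as a gap in specification. The analysis has a power figure but no rank, its split and test are not fixed, and no error control is described. The error cannot be given as one number. It is about 0.10, 0.17 or mostly 0.22 to 0.27 for two, four or eight tests, assuming 0.05 per test and splits unrelated to change. That second assumption favours the plan: with a shared averaged baseline, even one unadjusted interaction rejects about 0.07 to 0.32 of the time under no effect, for assumed reliability 0.95 to 0.5. Fixing the number of tests is therefore not enough; the contrast also has to be placebo-adjusted. The whole-group tests are not affected by this point.

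**What to change.** In the synopsis and 5.7, and repeated in 5.6 and 5.6.2:

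- Label the median-split analysis exploratory and hypothesis-generating.
- Use the M100 split for M100 latency and the gamma split for gamma, and name the gamma measure; the synopsis says power, 5.7 says activity.
- Name one test per outcome: the interaction of Group with STX209-minus-placebo change, split on the average of the three pre-dose baselines, reported as an estimate with a 95% CI. This also matches the placebo comparison in 2.1.
- State that a significant change within the impaired half is not evidence of a subgroup effect.
- State that the closing sentence of 5.7 refers only to the whole-group tests, and give the SD behind the 0.80.

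No procedure or sample size changes. A positive subgroup result can then be reported only as hypothesis-generating. The interaction estimate is also less precise, with a standard error about 1.3 to 1.7 times larger under the simple error model above, so the 0.80 would not carry over to it.
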